The protected health information will not be reused or disclosed to any other person or entity, except as required by law, for authorized oversight of the research study, or for other research for which the use of disclosure of PHI for which an authorization or opportunity to agree or object is not required by 45 CFR 164.512. The research could not be practicably conducted without the waiver, and without access and use of the PHI for recruitment.

9) Compensation to the Subjects

Subjects will be compensated \$10 per session. If the patient decides not to participate in further sessions, they will still receive the compensation for the completed sessions. Travel expenses up to \$30 per patient will be provided if needed. The compensation will be in the form of a gift card and will be given at the time of the visit.

PROTOCOL TITLE: Safety and feasibility of using low frequency deep brain stimulation of the subthalamic nucleus to improve cognitive performance in patients with Parkinson's disease

10) Study Timelines

The duration of the study from subject enrollment of the first patient to final data analysis will be approximately two years. Each individual subject will participate in the study for a maximum of 2 months for a total of 3 on-site experimental sessions and one telephone call. The first on-site visit will occur within the month prior to their planned DBS placement surgery, following the pre-operative visit. The second and third on-site visits will occur within the fourth week after the DBS electrode placement surgery, 3-4 days apart. A telephone call will be made 24 hours prior to the third on-site session to obtain additional safety information (Figure 1). Each participant will remain in the study for approximately 2 months from the time of consent. Participation is on a voluntary basis and subjects will reserve the right to withdraw participation in the study at any point of time. We expect the duration to enroll all study subjects will be approximately 2 years based on the number of patients who meet the inclusion and exclusion criteria.

We expect to complete the study by July 2017. The data will be analyzed as individual patients complete the study with further analyses after data collection is complete.

11) Study Endpoints

1. Safety: Safety endpoints will be measured by neuropsychiatric, motor, and cognitive testing:

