without stimulation and will complete the BDI. Informers will complete the NPI. Subsequently, the stimulators will be turned on, and each patient will repeat cognitive testing under gamma frequency (~130 Hz) and theta frequency stimulation (~5 Hz). The order of stimulation will be randomized. Stimulation will occur for 5 minutes prior to and continuously throughout each task. Amplitude and pulse width will be set to 3 V and 120 microseconds accordingly (Laxton & Lozano 2013) or as tolerated by the patient, and will remain constant across sessions. We will wait 20 minutes between testing conditions to elicit about 75% of DBS effects (Temperli et al 2003). At the end of the experimental testing session, the stimulator will be turned off or set to LFS in preparation for the second experimental session.

The second on-site experimental testing session will assess the effects of continuous theta stimulation on cognitive function. Patients will repeat cognitive testing after 48 hours of continuous theta stimulation. This second on-site testing session will occur 3-5 days following the first experimental session. Two days prior to the testing session, patients' stimulators will be turned on to the theta frequency stimulation setting and patients will return home and engage in normal activities. After 48 hours they will return to the clinic and repeat cognitive testing with continuous theta frequency stimulation. The UPDRS, NPI, and BDI will also be performed at this time. At the end of the session, their stimulators will be turned off.

We will screen for psychological changes by telephone once during the 2 day stimulation period. The patient will complete the BDI and a relative or caregiver will complete the NPI over the phone.

The structure of the experimental sessions is shown in Figure 2 and Figure 3.

[figure not shown]

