Safety data will include performance on psychological screening tests, cognitive tests, and motor tests. Efficacy data will include performance on cognitive tests. All data will be reviewed by a safety committee as described above. If any patient develops motor effects that are uncomfortable, the study will be halted for that particular subject. Furthermore, if the patient develops worsening psychological effects as measured through psychological screening tools, the study will be halted and the patient will be referred for appropriate care through the departments of Psychiatry and Neurology at UC Davis.

Safety information will be collected at study visits and with a telephone call. It will be saved in the database established for this study.

Safety data for motor effects will be collected prior to the patient's surgery and at the final study visit. Psychological data will be collected prior to DBS placement, at the first study visit, by phone call during the sustained frequency stimulation period, and at the final clinic visit.

The principal investigator and study members will review the data after each clinic visit and telephone contact with the patient. A safety committee will review the data after the first 4 patients, 8 patients, 12 patients, and 20 patients. The committee will include the PI, [name] in addition to [name], [name], and [name]. [name] is a neurologist, co-director of the DBS group, and has participated in multiple clinical trials involving the Parkinson's disease population. [name] is an expert in neurocognitive assessment in Parkinson's disease and has experience in identifying study related neurocognitive effects in clinical trials in dementia.

Data will be analyzed and evaluated in cohorts of 4 patients through the first 12 patients to determine whether subjects remain safe. This means we will evaluate the safety data from the first 4 patients before proceeding with subsequent subjects. We will evaluate data again after a total of 8 patients, 12 patients, and 20 patients.

PROTOCOL TITLE: Safety and feasibility of using low frequency deep brain stimulation of the subthalamic nucleus to improve cognitive performance in patients with Parkinson's disease

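### Individual stopping rules cover motor and psychological worsening but not clear cognitive worsening in a patient who can still be tested, and on one reading of the schedule home low-frequency stimulation starts before anyone has reviewed the scores (minor, cheap to fix)

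*Combined protocol and SAP*

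**What the plan says.** **Cognition is a safety domain.** Section 11 states: "Safety endpoints will be measured by neuropsychiatric, motor, and cognitive testing". Section 15 repeats it: "Safety data will include performance on psychological screening tests, cognitive tests, and motor tests". Aim 1 in section 4 says the same. Section 17 (Neurological Risk) accepts that longer ventral STN stimulation might make cognition worse for a time in some patients.

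**Individual rules.** Section 15 stops a subject who has uncomfortable motor effects or whose psychological screening worsens. Section 14 ends participation at a BDI of 20 or more. Section 16 adds psychological change that worries the patient, caregiver or tester. For cognition, section 15 promises only an analysis of reaction times and errors, and section 16 withdraws patients who cannot do the tests because of effort or altered mental status.

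**Reviews.** Under section 15 the principal investigator and team look at the data after each visit and call, and a safety committee reviews after 4, 8, 12 and 20 patients. No cognitive criterion is attached to either review.

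**Schedule.**
- Section 10, on spacing: "The second and third on-site visits will occur within the fourth week after the DBS electrode placement surgery, 3-4 days apart".
- Section 12, on spacing: "This second on-site testing session will occur 3-5 days following the first experimental session".
- Section 12, at the end of E1: "the stimulator will be turned off or set to LFS in preparation for the second experimental session".
- Section 12, two days before E2: "stimulators will be turned on to the theta frequency stimulation setting and patients will return home and engage in normal activities".
- Figure 2 legend: LFS goes on when E1 ends and lasts 48 hours.
- Section 10, on the timing of the call: "A telephone call will be made 24 hours prior to the third on-site session to obtain additional safety information".
- Section 14 places the telephone screening at 24 h of LFS. The call collects BDI and NPI, with no cognitive test.
- Stimulation is switched off when E2 ends.

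**The concern.** E1 is the only scheduled cognitive test under LFS before the patient takes LFS home. If a patient's Stroop, N-back and fluency results are clearly worse at E1 but testing is still possible, nothing in the plan tells staff to withhold the longer exposure. If LFS is set before the patient leaves E1, the review that might catch the decline comes afterwards. A halt at E2 is too late to change any study exposure, because stimulation then ends anyway. What is at stake is an avoidable period of home stimulation for such a patient, and an unclear exposure time in the part of the study meant to describe sustained LFS.

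**Working it through.** The plan gives no threshold, power or rate on this point, so there is no planned figure to reproduce. The check compares the rules, then the timings.

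**1. Rules by domain**

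| Domain | Individual stop for worsening | Where |
|---|---|---|
| Motor | Yes, on discomfort, no numeric threshold | Section 15 |
| Psychological | Yes, including BDI of 20 or more | Sections 14, 15, 16 |
| Cognitive | Only if the patient cannot be tested | Section 16 |

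A measured decline short of untestability meets no rule.

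**2. Timing by route.** Inputs: E2 at 3 to 5 days after E1 (section 12) or 3 to 4 (section 10); 48 h of home LFS; call 24 h before E2 (section 10).

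*Off after E1, on two days before E2:*
- Time for review = (3 to 5) − 2 = 1 to 3 days; under section 10, (3 to 4) − 2 = 1 to 2 days.
- LFS at the call = 48 − 24 = 24 h, which agrees with section 14.

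*LFS set as E1 ends:*
- Time for review before home LFS = 0 days.
- If LFS stops at 48 h, it ends 72 − 48 = 24 h to 120 − 48 = 72 h before E2, so E2 is not tested under continuous LFS as section 12 requires.
- If LFS runs on to E2, it lasts 3 × 24 = 72 h to 5 × 24 = 120 h (72 to 96 h under section 10), not 48 h.
- In that second case the call falls 72 − 24 = 48 h to 120 − 24 = 96 h after switch-on (48 to 72 h under section 10), not 24 h.

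Taken alone, the legend implies E2 two days after E1, which neither stated spacing allows.

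**3. Exposure.** Section 12 says: "Stimulation will occur for 5 minutes prior to and continuously throughout each task". With the single 5-minute lead-in shown in Figure 2 and about 30 minutes of testing, acute LFS is 5 + 30 = 35 min. Home LFS is 48 × 60 = 2,880 min, and 2,880 / 35 ≈ 82. This is a ratio of exposure, not of harm.

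**4. What a halt can still avoid (off-then-on route).** Before switch-on: up to 48 h. At the call: 48 − 24 = about 24 h, but only through patient or caregiver concern, since no cognitive score is taken. At E2: 0 h.

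**5. Chance halts, by form of rule.** Illustration only. Assumptions: no true LFS effect, three independent tests, each wrongly flagged with probability p per patient.
- Any one of three: 1 − (1 − p)³. At p = 5%: 1 − 0.95³ = 14.3%, about 2.9 of 20. At p = 1%: 3.0%, about 0.6 of 20.
- At least two of three: 3p²(1 − p) + p³. At p = 5%: 0.007125 + 0.000125 = 0.7%, about 0.15 of 20. At p = 1%: 0.03%, about 0.006 of 20.

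Tests taken in one sitting are probably correlated, which would narrow this gap.

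**The case against.** A reader might infer three things that the documents do not support.

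- **That cognition has no individual stop at all.** Section 16 provides one for gross failure: patients who cannot be tested are withdrawn.
- **That cognitive worsening goes unwatched.** Section 4 says that testing in cohorts of four is meant to pick up negative effects on performance before more patients are enrolled. The committee includes a neurocognitive expert, and data are reviewed after every visit. The principal investigator may both give the tests and reprogram the generator (section 24), permission is sought at each session (section 29), and the caregiver NPI is taken during home LFS.
- **That motor safety is better monitored.** The motor rule is subjective, and motor safety data are scheduled only before surgery and at the final visit. Cognition is scored at baseline, three times at E1 and once at E2. The contrast is between stated rules, not between strong and weak monitoring.

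It can also be said that the main text of section 12 sets switch-on two days before E2, that sections 10 and 14 agree with it, and that this leaves time for review. The named risk is temporary and concerns prolonged stimulation, which a test of about 35 minutes may not predict. Withholding patients who worsen acutely also removes informative cases from the sustained-LFS data.

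All of this limits the point, but the gap remains. Cohort review protects later patients, not the one being tested. The post-visit review has no cognitive trigger. Section 12 also allows LFS to be set at the end of E1, and the Figure 2 legend prescribes it.

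**Conclusion.** The point holds as a minor one. Two things stand on the text: there is no individual halting rule for clear cognitive worsening short of inability to be tested, and the Figure 2 legend cannot be reconciled with the spacing of E1 and E2 given elsewhere.

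The timing part is conditional: home LFS precedes the review only if LFS is set as E1 ends. It would be wrong to say that every patient goes home unreviewed.

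Up to 20 patients are concerned. The documents give no rate of worsening, so the number affected is unknown. The benefit of a check at E1 rests on the assumption that acute worsening says something about sustained worsening, which the documents do not state. A reader might also want any drop on one test to halt the patient. The documents do not support that, and the illustration above shows that such a rule would stop patients by chance more often.

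**What to change.** 1. Align the Figure 2 legend, and the section 12 option to set LFS at the end of E1, with the main text of section 12: LFS starts 48 h before E2 and the call falls at 24 h of LFS. Use one E1-to-E2 spacing in sections 10 and 12.
2. Have existing staff compare the E1 no-stimulation and acute-LFS scores before LFS is set for home use.
3. Add to section 15, beside the motor rule, that a subject is halted for clear cognitive worsening under LFS in the investigator's judgement. This would normally show on more than one test or come with patient or caregiver concern; a drop on one test alone would not be enough.
4. Report any patients withheld to the safety committee and with the Aim 3 results.

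**Cost.** Mostly wording, plus a look at scores already collected; no new test. Section 12 already implies a switch-on contact two days before E2, but section 10 counts only three on-site sessions, so the plan should say where that contact takes place.

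**Downsides.** No-stimulation testing always comes first, so fatigue or carry-over may cause an occasional unnecessary halt, and practice may hide a decline. Sustained-LFS data are lost for patients withheld, and Aim 3 then describes only those who went on to home LFS. A judgement-based rule, like the motor rule, does not set one threshold for all patients.

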- (1) Adult men and woman with a diagnosis of PD.
- (2) Patients who are candidates for bilateral STN DBS placement surgery and who will receive this treatment as part of their routine care.
- (3) Willingness to undergo temporary changes in STN DBS generator settings.

PROTOCOL TITLE: Safety and feasibility of using low frequency deep brain stimulation of the subthalamic nucleus to improve cognitive performance in patients with Parkinson's disease

(4) Patients who have a caregiver who is willing to answer psychological screening questions on behalf of the patient.

Exclusion criteria:

- (1) Patients less than 18 years of age.
- (2) Patients who are not candidates for bilateral STN DBS placement surgery.
- (3) Adults unable to consent
- (4) Pregnant woman
- (5) Prisoners
- (6) Patients who score over 20 on the BDI indicating moderate depression

7) Number of Subjects

The target sample size is 22 subjects. The study design is a phase 1 safety and feasibility study. While results may show a trend towards efficacy, we will not be able to power the study toward efficacy. Two of these subjects will be used to evaluate the ease of use of the computerized cognitive test, but will not participate in any other study procedures and data will not become part of the study record. All subjects are to be enrolled locally at UC Davis medical center.

8) Recruitment Methods

a) Study-Wide:

NA

b) Local:

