to rely on connections between the basal ganglia and the prefrontal cortex (Dadgar et al 2013, Jaywant et al 2014). Furthermore, DBS has been shown in some studies to impair phonemic verbal fluency, which may or may not recover over time (Ehlen et al 2014, Wojtecki et al 2006, Wu et al 2014). These specific letters were chosen based on the frequency of English language words that begin with the letters (Borkowski et al 1967.)

Total testing time will be approximately 30 minutes per stimulation condition with 20 minutes between conditions, resulting in a total time of approximately 30 minutes for the baseline cognitive testing, 2 hours for the first experimental session and 30 minutes for the second experimental session. Additional time will be needed for setup and explanation of the task directions. Finally, 20 minutes of psychological screening will be performed at the baseline session, over the phone between experimental sessions 1 and 2, and following cognitive testing during experimental session 2.

Baseline Testing: 30 min cognitive testing, 20 minute psychological screening (Total Time: approximately 50 min)

Experimental Session 1: 20 minutes psychological screening, 2 hours cognitive testing (Total Time: approximately 2h 20 min)

Phone call between experimental session 1 and 2: 20 minutes psychological screening

Experimental Session 2: 30 min cognitive testing, 20 minute psychological screening, 20 min motor screening (Total Time: approximately 70 minutes)

b) Humanitarian Use Device (HUD)

NA

13) Data and Specimen Banking

No data or specimens will be retained longer than required by law or hospital policy.

14) Data Management and Confidentiality

The target sample size is 22 subjects. The study design is a safety and feasibility phase 1 study. While results may show a trend towards efficacy, we will not be able to power the study toward efficacy.

Safety Data Analysis:

To examine possible effects on motor symptoms, we will screen for changes in the motor section of the UPDRS score after sustained LFS. After each patient is tested, we will calculate individual changes in UPDRS scoring. After the entire patient population is tested, we will use T-tests to determine if there is a significant change in the overall rating scale.

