We will also examine changes in psychological symptoms. For each individual patient, we will measure the BDI and NPI at baseline, at the first experimental session, by phone call after 24 h LFS, and at the final experimental session. For the BDI, we will consider any score greater or equal to 20 as evidence of moderate depression and will terminate the study for any individual that shows evidence of depression. At the group level, we will calculate

PROTOCOL TITLE: Safety and feasibility of using low frequency deep brain stimulation of the subthalamic nucleus to improve cognitive performance in patients with Parkinson's disease

the percentage of people that develop depression. For the NPI, we will calculate the total score. At the individual level we will look for the development of new symptoms in the 12 subsections. At the group level we will perform an ANOVA to look for significant changes across the 3 time points.

Cognitive Data Analysis:

The cognitive data analysis will examine the effect of theta frequency stimulation on cognitive task performance. Analyses for the Stroop task will include the examination of response time and error rates across stimulator settings. Two (trial type: congruent vs incongruent) by three (Setting: low, high, no stimulation) ANOVAs will be performed for both reaction time and accuracy. Post conflict and post error reaction time adjustments will also be examined across stimulator settings. For the N-back test, ANOVAs will also be performed to assess the effects of complexity (1,2-back) and stimulation frequency (none, high, low) on error rates. For the verbal fluency test, the average number of words generated across stimulation conditions and the change in word number on low and high frequency stimulation settings will be compared. Analyses will be performed using MATLAB and STATA.

Describe any procedures that will be used for quality control of collected data.

a.) Study-Wide:

NA

b.) Local

Describe the local procedures for maintenance of confidentiality.

This research is partly funded by a donation from the Chevo Foundation. The Chevo Foundation will not have access to any of the study documents including the data.

Data files to be stored include group assignment, background information, any head scans if performed, and results from neurocognitive and motor tests.

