Safety Data Analysis: To examine possible effects on motor symptoms, we will screen for significant changes in the motor section of the UPDRS score after sustained LFS. After each patient is tested, we will calculate individual changes in UPDRS scoring. After the entire patient population is tested, we will use a T-test to determine if there is a significant change the motor section.

We will also examine changes in psychological symptoms using the BDI and NPI. We will examine percentage of people who convert to moderate depression as indicated by a BDI score 20 or higher. We will also look for significant changes in the BDI and NPI across time using ANOVAs.

Changes in cognition will also be analyzed by looking at reaction time and error rates on different cognitive tests as described previously.

- Any conditions that trigger an immediate suspension of the research.

None.

16) Withdrawal of Subjects

Describe anticipated circumstances under which subjects will be withdrawn from the research without their consent.

Patients unable to perform cognitive tests due to effort or altered mental status.

Patients who experience any change in psychological symptoms that is concerning to the patient, caregiver, or test administrator as assessed through psychological screening tools.

Describe any procedures for orderly termination.

The patient is not undergoing any additional procedures, except for stimulation and cognitive testing.

Describe procedures that will be followed when subjects withdraw from the research, including partial withdrawal from procedures with continued data collection.

Patients' data will be recorded, unless specifically asked to be withdrawn

Patients will continue to be followed for medical management

17) Risks to Subjects

Physical Risk:

- There is minimal to no physical risk. Once the patient's stimulation is turned off, the patient's pre-stimulation symptoms will likely return (Temperli et al 2003).
- There is a small chance that changes in affective symptoms including dysphoria, depression, mania, or psychosis may occur (Smeding et al 2006, Strutt et al 2012). Patients will be carefully screened using standardized assessment tools.
- All cognitive and memory tests are designed to be minimally difficult and pose minimal

PROTOCOL TITLE: Safety and feasibility of using low frequency deep brain stimulation of the subthalamic nucleus to improve cognitive performance in patients with Parkinson's disease

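### A patient halted for motor effects before the final session has no planned post-LFS UPDRS and is not counted, so the group motor t-test leans toward no change

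*Combined protocol and SAP*

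**What the plan says.** All references are to the combined protocol and SAP.

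- **Size (section 7).** "The target sample size is 22 subjects". Two of them only try out the computerized test, which leaves 20. No power or precision target is set: "While results may show a trend towards efficacy, we will not be able to power the study toward efficacy".
- **Motor measurement (section 15).** "Safety data for motor effects will be collected prior to the patient's surgery and at the final study visit". Section 11 gives the same two times.
- **Sustained LFS (section 12).** Patients spend about 48 hours at home on LFS before E2. The one planned contact in that time is a telephone call at about 24 hours, with BDI and NPI but no motor measure.
- **Stopping an individual.** For motor effects, section 15: "If any patient develops motor effects that are uncomfortable, the study will be halted for that particular subject". For psychological effects, section 15: "if the patient develops worsening psychological effects as measured through psychological screening tools, the study will be halted". For a BDI of 20 or more, section 14: "will terminate the study for any individual that shows evidence of depression". Section 16 also withdraws patients with a worrying psychological change on the screening tools, and this group: "Patients unable to perform cognitive tests due to effort or altered mental status".
- **Group analysis.** Section 14: "After the entire patient population is tested, we will use T-tests to determine if there is a significant change in the overall rating scale". Section 15 repeats the t-test for the motor section of the scale. NPI (sections 14 and 15) and BDI (section 15) are compared over time by ANOVA. Depression is reported as a percentage of patients.
- **After withdrawal (section 16).** Data already obtained are kept unless the patient asks otherwise, and medical follow-up continues. No further study assessment is mentioned.

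**The concern.** Aim 1 is to monitor the psychological, cognitive and motor consequences of LFS. For the motor part, the group result is a change score that needs a value at E2. The halting rule removes patients because of a motor effect, and most of the exposure to LFS falls in the home period, before that value is taken. The missing data are therefore caused by the outcome being measured, and what remains describes patients who tolerated LFS.

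A count of motor halts would let a reader see this, but none is defined. Depression is the only harm reported as a proportion of patients. A group finding of no motor change could then mean that LFS is benign, or that the patients it affected were absent. The results are meant to inform a phase 2 study, where that difference matters.

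**Working it through.** **1. What can be reproduced.** 22 − 2 = 20 study patients. No alpha, power, effect size, SD or halt rate is given, so no further figure in the plan can be checked. The core of the point is structural.

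**2. Schedule against analyses**, for a patient halted during home LFS who does not attend E2:

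| Group analysis | Values needed | Is the halted patient in it? |
|---|---|---|
| UPDRS t-test | pre-surgery and E2 | No |
| Cognition after sustained LFS | E2 | No |
| BDI and NPI ANOVAs | baseline, E1, 24-hour call, E2 | Unclear: out if complete cases are required, in if all available values are used |
| Stroop and N-back ANOVAs (low, high, none) | the three settings tested at E1 | Yes |
| Percentage developing depression | any BDI | Yes, counted if the 24-hour BDI meets the criterion |
| Motor halts | a count | Not defined |

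For the NPI ANOVA, section 14 names three time points although four are scheduled, and does not say which three.

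**3. Bias in the mean.** Let k of n patients be halted, with mean change mH, and let mO be the mean change in those observed. Then:

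full mean = [(n − k)·mO + k·mH]/n, so full mean − mO = (k/n)·(mH − mO).

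With n = 20 and an assumed difference mH − mO (the documents give none), the understatement in UPDRS points is:

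| Halted | difference 10 | difference 15 |
|---|---|---|
| 1 | 1/20 × 10 = 0.5 | 0.75 |
| 2 | 1.0 | 1.5 |
| 3 | 1.5 | 2.25 |
| 4 | 2.0 | 3.0 |

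**4. Chance that it arises.** P(at least one halt) = 1 − (1 − p)^20. For assumed p of 5%, 10%, 15% and 20% this is 64%, 88%, 96% and 99%.

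**5. Effect on the t-test.** Simulation with 100,000 trials, n = 20, normal change scores with SD 1, and a two-sided 5% one-sample t-test. The assumed true mean worsening is 0.65 SD, for which power is 79% with all 20 patients.

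| Missing | Observed mean (SD), worst patients lost | Power, worst lost | Power, halting correlated 0.5 with change | Power, lost at random |
|---|---|---|---|---|
| 1 | 0.55 | 69% | 71% | 77% |
| 2 | 0.47 | 58% | 64% | 74% |
| 3 | 0.39 | 47% | 56% | 71% |
| 4 | 0.32 | 37% | 48% | 68% |

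The gap between the last column and the two before it is due to selection, not to the smaller sample. With no true mean change, losing the worst 1 to 4 patients raises the chance of a falsely significant improvement from 2.5% to 7%, 15%, 26% and 38%.

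**The case against.** A reader might infer that all of the Aim 1 group safety analyses exclude the patients whom LFS harmed most. The documents do not support that.

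- **Cognition.** LFS is also tested acutely at E1, and the specified cognitive ANOVAs compare the three E1 settings. A patient halted later keeps those data. Only the score after sustained LFS is lost, and no ANOVA names it as a level.
- **Mood.** Psychological halts rest on BDI or NPI results, which are kept. The depression percentage counts a patient stopped on the 24-hour BDI, and new NPI symptoms are examined patient by patient.
- **Mental status.** That rule applies when cognitive testing is attempted. No cognitive test is done at home or by telephone, so it is not a route out of the study during home LFS.
- **Attendance.** No section says that halted patients skip E2. It is the natural reading of halting and terminating, but it remains an inference. The firm defect is the missing rule.
- **Oversight.** Individual UPDRS changes are calculated, data are reviewed after every contact, and a committee reviews after 4, 8, 12 and 20 patients. A halt would be visible to them.
- **The test itself.** It compares pre-surgery with post-surgery scores in an unpowered study, so it does not isolate LFS even with complete data.

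All of this stands, and it confines the point mainly to the motor result. It does not answer it. Review of individuals can detect a harm but does not correct the group estimate, and a before-after comparison that is already hard to interpret becomes harder when the affected patients are missing from it.

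**Conclusion.** The point holds for the group UPDRS t-test. Followed as written, and on the natural reading of the halt, the test omits patients halted for motor effects before E2, no count replaces them, and the result is biased toward no change. The score after sustained LFS is affected in the same way, and so are the BDI and NPI ANOVAs if run on complete cases. The E1 cognitive ANOVAs and the depression percentage are not.

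The direction follows from the documents, provided that halted patients have worse motor change than the rest. The size does not: the halt rate, the point difference, the SD-scale effect and the correlation are all assumptions, and the plan never ties uncomfortable motor effects to UPDRS points. Under them, 1 to 4 halts hide 0.5 to 3.0 points of mean worsening and cut power from 79% to between 71% and 37%, depending on how closely halting follows motor change. It would be too strong to say that the whole effect disappears. That is so only if every patient who worsens is halted and nobody else changes.

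**What to change.** Leave the halting and withdrawal rules as they are, and change what is counted, analysed and recorded.

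1. **Count.** Report the number and percentage halted or withdrawn by reason (motor, psychological, mental status, other) as a safety outcome beside the t-test. Use two denominators: all patients who started LFS, and those who started sustained LFS.
2. **Analyse.** Add a sensitivity analysis of UPDRS change in which halted patients receive the worst rank, for example with a signed-rank test. In the BDI and NPI analyses use all available values, including the 24-hour call, and state which time points the NPI analysis covers.
3. **Record.** Where the patient agrees and switch-off is not delayed, record the UPDRS motor section at the halt contact, with the hours of LFS received and whether stimulation was on or off. The full E2 set is not realistic here: section 12 allows 30 + 20 + 20 = 70 minutes for it, of which the motor part is 20.

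The depression criterion must also be reconciled before halts are tabulated: section 11 counts scores above 20, sections 14 and 15 count 20 or more.

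The cost is a few sentences in sections 14 to 16 and, for a halted patient, about 20 minutes with an instrument already planned. The downside is that some halt assessments will be partial, earlier than 48 hours or off stimulation, and that the worst-rank result is conservative. It should therefore sit beside the main analysis and not replace it.
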